8.2.6 Visit 6 / Day 28 (±4 days)

Subjects should present to this study visit in the fasted state (minimum 8-hour overnight fast).

The following predose procedures/assessments will be conducted:

- Collect and Review Daily Dosing Log.
- Draw and process blood samples for laboratory tests (Section 11.5):
 - Hematology (CBC)
 - Comprehensive metabolic panel (includes LFT as well as routine chemistry panel; glucose, CPK, magnesium)
 - o Glycated albumin
 - o hs-CRP
 - o LDL, VLDL, HDL, FFA, total cholesterol, and triglycerides
 - \circ ApoB and Lp(a)
 - o HOMA-IR includes glucose, insulin, and C-peptide
 - o PEth test
- Collect and process urine sample for laboratory tests (Section 11.5):
 - Routine UA (dipstick)
 - Pregnancy test (female subjects)
 - Drug screen
- Draw and process blood samples for PD assessments:
 - OWL metabolomics and OWL lipidomics (Section 10.4)
 - SomaScan proteomics (Section 10.5)
 - Exploratory biomarkers (Section 10.7)
- Draw and process blood sample for PK (Section 9.1).
- Perform targeted physical examination including a neurological examination (Section 11.2).
- Measure and record vital signs including the InBody scale (Section 11.3).
- Perform 12-lead ECG (Section 11.6).
- Record AEs and concomitant medications.

Administer study drug (Section 6.2.1) after completion of all predose assessments. Conduct the following **postdose procedures/assessments:**

- Draw and process blood samples for PK (Section 9.1) at approximately 2, 4, and 6 hours postdose.
- Measure and record vital signs (Section 11.3) prior to discharge.
- Record AEs and concomitant medications.

- Dispense study drug.
- Dispense Daily Dosing Log.

8.2.7 Visit 7 / Day 42 (±4 days)

Subjects should present to this study visit in the fasted state (minimum 8-hour overnight fast).

The following predose procedures/assessments will be conducted:

- Collect and Review Daily Dosing Log.
- Measure and record vital signs including the InBody scale (Section 11.3).
- Perform 12-lead ECG (Section 11.6).
- Record AEs and concomitant medications.
- Perform targeted physical examination including a neurological examination (Section 11.2).
- Collect urine sample for pregnancy test (female subjects [Section 11.5]).
- Draw and process blood sample for glycated albumin (Section 11.5).
- Draw and process blood sample for PK (Section 9.1).

After completing predose assessments:

- Administer study drug (Section 6.2.1).
- Dispense study drug.
- Dispense Daily Dosing Log.

8.2.8 Visit 8 /Day 49 (±2 days)

The following procedures will be conducted:

- Collect and Review Daily Dosing Log.
- Measure and record vital signs including the InBody scale (Section 11.3).
- Record AEs and concomitant medications.
- Administer study drug (Section 6.2.1).
- Dispense study drug.
- Dispense Daily Dosing Log.

8.2.9 Visit 9 / Day 61

Visit 9 may be split into multiple visits to allow for conduct of all procedures and assessments. The allowable visit windows along with specific assessments/procedures to be conducted within these visit windows is detailed below.

8.2.9.1 Visit 9a / Day 61 (±1 day)

On Study Day 61 (± 1 day), the following assessments will be conducted:

Subjects should present to this study visit in the fasted state (minimum 8-hour overnight fast).

The following predose procedures/assessments will be conducted:

- Collect and Review Daily Dosing Log.
- Draw and process blood samples for laboratory tests (Section 11.5):
 - Hematology (CBC)
 - Comprehensive metabolic panel (includes LFT as well as routine chemistry panel; glucose, CPK, magnesium)
 - o HbA_{1c}
 - Glycated albumin
 - hs-CRP
 - o LDL, VLDL, HDL, FFA, total cholesterol, and triglycerides
 - \circ ApoB and Lp(a)
 - HOMA-IR includes glucose, insulin, and C-peptide
- Collect and process urine sample for laboratory tests (Section 11.5):
 - Routine UA (dipstick)
 - Pregnancy test (female subjects)
 - Drug screen
- Draw and process blood samples for PD assessments:
 - OWL metabolomics and OWL lipidomics (Section 10.4)
 - SomaScan proteomics (Section 10.5)
 - ELF assay (Section 10.6)
 - Exploratory biomarkers (Section 10.7)
- Draw and process blood sample for PK (Section 9.1).
- Perform complete physical examination including a neurological examination (Section 11.2).
- Measure and record vital signs including the InBody scale (Section 11.3).
- Perform 12-lead ECG (Section 11.6).
- Record AEs and concomitant medications.
- Administer study drug (Section 6.2.1) if the visit occurs on Day 61. For those subjects whose visit occurs on Day 62, the last dose should be taken on Day 61, with no drug administered on Day 62.

8.2.9.2 Visit 9b / Day 61 (-4 days to + 1 day)

• Perform MRI/MRI-PDFF (Section 10.1).

8.2.9.3 Visit 9c / Day 61 (-5 days to + 2 days)

• Perform Fibroscan (Section 10.3).

8.2.9.4 Visit 9d / Day 61 (-5 days to + 7 days)

• Perform Ophthalmologic examination (Section 11.3).

8.2.10 Visit 10/ Day 73 (±2 days)

The following procedures will be conducted during the follow-up visit:

- Collect and process urine sample for laboratory tests (Section 11.5):
 - Routine UA (dipstick)
 - Pregnancy test (female subjects)
- Draw and process blood samples for laboratory tests (Section 11.5):
 - Hematology (CBC)
 - Comprehensive metabolic panel (includes LFT as well as routine chemistry panel; glucose, CPK, magnesium)
- Draw and process blood sample for PK (Section 9.1).
- Perform targeted physical examination including a neurological examination (Section 11.2).
- Measure and record vital signs including the InBody scale (Section 11.3).
- Perform 12-lead ECG (Section 11.6).
- Record AEs and concomitant medications.

8.2.11 Early Termination Visit

The early termination visit assessments is based on whether the subject completed < 28 days or ≥ 28 days of treatment. Recognizing that subjects may refuse to complete all the assessments for early termination, the procedures have been arranged in the order of prioritization.

For < 28 days of dosing, the following early termination visit procedures will be conducted:

Subjects should present to this study visit in the fasted state (minimum 8-hour overnight fast).

The following procedures/assessments will be conducted:

- Collect and Review Daily Dosing Log.
- Draw and process blood samples for laboratory tests (Section 11.5):
 - Hematology (CBC)
 - Comprehensive metabolic panel (includes LFT as well as routine chemistry panel; glucose, CPK, magnesium)
 - o HbA_{1c}
 - o Glycated albumin

- Collect and process urine sample for laboratory tests (Section 11.5):
 - Routine UA (dipstick)
 - Pregnancy test (female subjects)
- Draw and process blood sample for PK (Section 9.1).
- Perform targeted physical examination including a neurological examination (Section 11.2).
- Measure and record vital signs including the InBody scale (Section 11.3).
- Perform 12-lead ECG (Section 11.6).
- Record AEs and concomitant medications.
- Perform Ophthalmologic examination (Section 11.3) (only if subject has been dosed for \geq 14 days).
- Perform Fibroscan (Section 10.3).

For \geq 28 days of dosing, the following early termination visit procedures will be conducted:

Subjects should present to this study visit in the fasted state (minimum 8-hour overnight fast).

The following procedures/assessments will be conducted:

- Collect and Review Daily Dosing Log.
- Perform complete physical examination including a neurological examination (Section 11.2).
- Draw and process blood samples for laboratory tests (Section 11.5):
 - Hematology (CBC)
 - Comprehensive metabolic panel (includes LFT as well as routine chemistry panel; glucose, CPK, magnesium)
 - o HbA_{1c}
 - o Glycated albumin
 - o hs-CRP
 - o LDL, VLDL, HDL, FFA, total cholesterol, and triglycerides
 - \circ ApoB and Lp(a)
 - HOMA-IR includes glucose, insulin, and C-peptide
- Collect and process urine sample for laboratory tests (Section 11.5):
 - Routine UA (dipstick)
 - Pregnancy test (female subjects)
- Draw and process blood samples for PD assessments:
 - OWL metabolomics and OWL lipidomics (Section 10.4)
 - SomaScan proteomics (Section 10.5)
 - ELF assay (Section 10.6)

- Exploratory biomarkers (Section 10.7)
- Draw and process blood sample for PK (Section 9.1).
- Measure and record vital signs including the InBody scale (Section 11.3).
- Perform 12-lead ECG (Section 11.6).
- Record AEs and concomitant medications.
- Perform Ophthalmologic examination (Section 11.3).
- Perform MRI/MRI-PDFF (Section 10.1).
- Perform Fibroscan (Section 10.3).

8.3 Concomitant Medications and Other Restrictions

8.3.1 Concomitant Medications

Subjects must be on stable doses of medications for underlying obesity-related conditions for at least 2 months prior to screening.

Subjects with diabetes may be treated with metformin, DPP-4 inhibitors, or sulfonylureas, but must be on stable doses for at least 2 months prior to screening.

Any concomitant medication use must have a strong clinical indication (i.e. treatment of AEs).

The following are expressly **prohibited** during the study:

- a) Any herbal supplement, over the counter drug, mail order or prescription drug for weight loss.
- b) Products with CBD.
- c) Prescription or over the counter stimulants including: dextroamphetamine/Dexedrine, dextroamphetamine/amphetamine combination product/Adderall, or methylphenidate (Ritalin®, Concerta®).
- d) Thiazolidinediones (TZD): pioglitazone/Actos, rosiglitazone/Avandia.
- e) Glucagon-like peptide 1 (GLP1) agonists: exenatide/Byetta/Bydureon, lixisenatide/Adlyxin, liraglutide/Victoza, dulaglutide/Trulicity, semaglutide/Ozempic.
- f) Sodium-glucose cotransporter-2 (SGLT2) inhibitors: canagliflozin/Invokana, dapagliflozinfarxiga, empagliflozin/Jardiance, ertugliflozin/Steglatro.
- g) Vitamin E: use of ursodiol or high dose vitamin E >400 IU/day for at least one month within in the last 6 months or started high dose vitamin E within last 3 months of screening.
- h) Obeticholic acid/Ocaliva, systemic corticosteroids, methotrexate, tamoxifen, amiodarone, or long-term use of tetracyclines.
- i) Warfarin, heparin, factor Xa inhibitors (dabigatran betrixaban edoxaban, apixaban, and rivaroxaban).

 j) Concomitant medications that prolong the QT/QTc interval and are known to be associated with increased risk of Torsade des pointes as identified in the https://crediblemeds.org/ website list category of 'Known Risk' (Appendix B).

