7.3 Exclusion Criteria

Subjects will be excluded from the study if any of the following criteria are met:

- 1. Insulin-controlled diabetes.
- 2. Pregnant or breastfeeding or plans to become pregnant.

- Intolerance to Magnetic Resonance Imaging (MRI) or with conditions contraindicated for MRI
 procedures including but not limited to inability to fit into MRI scanner or surgical clips/metallic
 implants/shrapnel. Subjects must not be claustrophobic, have a history of claustrophobia, or
 intolerance of closed or small spaces.
- 4. Weight gain or loss >5% in 3 months prior to study or >10% in 6 months prior to screening.
- 5. History of lap banding, intragastric balloon, duodenal-jejunal sleeve, or bariatric surgery within 5 years of screening, plans for bariatric surgery prior to conclusion of study participation, or plans to lose weight during this study either through a special diet, exercise program or *both*. Subjects currently maintained on a special diet or exercise program must be willing to discontinue that program for 30 days prior to Day 1 and throughout the duration of the study.
- 6. History of malignant hyperthermia.
- 7. History of chronic serious recurrent skin rashes of unknown cause.
- 8. History of or current clinically significant cardiovascular disease including but not limited to transient ischemic attack, stroke, cardiac arrhythmias, syncope, unstable angina, myocardial infarction in the 6 months prior to screening, congestive heart failure, or uncontrolled hypertension. (Uncontrolled hypertension is defined as a systolic blood pressure ≥160 mmHg or a diastolic blood pressure ≥100 mmHg).
- 9. Resting heart rate <45 or >110 bpm.
- 10. On screening ECG or by history:
 - a. A marked baseline prolongation of QT/QTcF interval (e.g., repeated demonstration of a QTcF interval > 450 msec for males and >470 msec for females).
 - b. A history of additional risk factors for *Torsades de Pointes* (TdP) (e.g., heart failure, hypokalemia, family history of Long QT Syndrome) or a family history of sudden cardiac death of unknown origin.
- Kidney disease, kidney transplant, or estimated glomerular filtration rate (eGFR) <50 mL/min/1.73 m² based on the CKD-EPI Creatinine Equation (NKF 2009; https://www.kidney.org/content/ckd-epi-creatinine-equation-2009).

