- 35. Participation in another clinical trial at the time of screening or exposure to any investigational agent, including topical, within 30 days of screening or 5 half-lives, if half-life known.
- 36. No tattoo or body piercings during the course of the study. Any underlying physical or psychological medical condition that, in the opinion of the Investigator or sponsor, would make it unlikely that the subject is able comply with the study requirements or would be unable to complete the study.
- 37. Any condition that the investigator believes would interfere with his/her ability to provide written informed consent, comply with study instructions, or which might confound the interpretation of the study results or put the subject at undue risk.
- 38. Known or potential hypersensitivity to HU6 or its excipients.

Prohibited Medications (Current Use):

- 39. Any herbal supplement, over the counter drug, mail order or prescription drug for weight loss.
- 40. Prescription or over the counter stimulants including: dextroamphetamine/Dexedrine, dextroamphetamine/amphetamine combination product/Adderall, or methylphenidate (Ritalin®, Concerta®).
- 41. Thiazolidinediones (TZD): pioglitazone/Actos, rosiglitazone/Avandia.
- 42. Glucagon-like peptide 1 (GLP1) agonists: exenatide/Byetta/Bydureon, lixisenatide/Adlyxin, liraglutide/Victoza, dulaglutide/Trulicity, semaglutide/Ozempic.

- 43. Sodium-glucose cotransporter-2 (SGLT2) inhibitors: canagliflozin/Invokana, dapagliflozin/Farxiga, empagliflozin/Jardiance, ertugliflozin/Steglatro.
- 44. Vitamin E: use of ursodiol or high dose vitamin E >400 IU/day for at least one month within in the last 6 months or started high dose vitamin E within last 3 months of screening.
- 45. Recent (within 3 months of screening) or current use of obeticholic acid/Ocaliva, systemic corticosteroids, methotrexate, tamoxifen, amiodarone, or long-term use of tetracyclines.
- 46. Warfarin, heparin, factor Xa inhibitors (dabigatran betrixaban edoxaban, apixaban, and rivaroxaban).
- 47. Concomitant medications that prolong the QT/QTc interval and are known to be associated with increased risk of Torsade des pointes as identified in the https://crediblemeds.org/ website list category of **'Known Risk'** (Appendix B). For subjects on medications that are listed in Appendix B, approval must be obtained from the Sponsor and Medical Monitor.

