13.1.2 Protocol Deviations

No deviations from the protocol are anticipated. Requests for deviations must be made in advance with the Sponsor. Should a non-anticipated protocol deviation occur, the Sponsor must be informed as soon as possible. All deviations and the reasons for the deviation will be documented by the Investigator or designated staff. Reporting of protocol deviations to the IRB and in accordance with applicable Regulatory Authority mandates is an Investigator responsibility.

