13.1.3 Protocol Waivers

Protocol waivers will not be granted by the Sponsor in this study.

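### Protocol 8.3.1(j) bars Appendix B torsade-risk drugs during the study without exception, but exclusion 47 lets subjects already taking them be approved for entry

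*Protocol*

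**What the plan says.** Three places in the protocol deal with drugs in the crediblemeds 'Known Risk' category, which Appendix B reproduces.

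- **Section 8.3.1, Concomitant Medications.** The list opens with "The following are expressly prohibited during the study". Item j is "Concomitant medications that prolong the QT/QTc interval and are known to be associated with increased risk of Torsade des pointes", with a pointer to Appendix B. It has no approval route or other exception. Item h separately lists amiodarone, also without exception.
- **Section 7.3, Exclusion Criteria, item 47.** The section opens with "Subjects will be excluded from the study if any of the following criteria are met". Item 47 sits under a subheading that labels current use of the listed drugs as prohibited. It describes the same class as 8.3.1(j) in almost the same words, then adds: "For subjects on medications that are listed in Appendix B, approval must be obtained from the Sponsor and Medical Monitor".
- **Synopsis, exclusion item 48.** Same criterion and same approval sentence as item 47.

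Exclusion 45 in Section 7.3 (synopsis item 46) excludes recent or current use of amiodarone and gives no approval route. Appendix B lists amiodarone.

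The SAP does not address the point. Its Section 10 defines prior medications to include those continued during the study, and concomitant medications as those started after the first dose. Its Section 13.5 tabulates QTcF increases of more than 30 and up to 60 msec, increases of more than 60 msec, and post-baseline values above 500 msec.

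**The concern.** A site with a candidate who takes an Appendix B drug needs two answers: may this person enrol, and may the drug continue during the 61 days of dosing? The eligibility section implies that both are possible with approval. The on-study section says that the drug may not be taken. A site that obtains the approval and acts on it is then out of compliance with the other section.

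This is a cardiac-safety rule in a trial that excludes subjects with prolonged QTcF or torsade risk factors (Section 7.3, item 10) and tabulates QTcF as a safety outcome. With up to 5 centers, the same kind of subject could be enrolled and kept on the drug at one site, asked to stop it at another, and refused at a third. Each site could point to protocol text in support. The same events could be recorded as protocol deviations at one site and not at another.

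**Working it through.** No figure is at issue, so the check sets the passages side by side and asks what each says for each type of subject.

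| Situation | Exclusion 47 / synopsis item 48 | Section 8.3.1 | Consistent? |
|---|---|---|---|
| A. On an Appendix B drug at entry, no approval | Excluded | Not reached | Yes |
| B. On such a drug at entry, approved, stops before first dose | Enrolled | Not breached during dosing | Yes, but no text requires the stop |
| C. On such a drug at entry, approved, continues | Enrolled with approval | Prohibited by item j | **No** |
| D. Starts such a drug after first dose | An entry criterion; does not naturally apply | Prohibited by item j | Yes; one rule governs |
| E. On amiodarone at entry | Approval route, because it is in Appendix B | Prohibited by items h and j | **No**; exclusion 45 also bars it with no approval route |

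**Row C.** The two texts cover the same set of drugs: both refer to the 'Known Risk' category and both cite Appendix B. The only substantive difference is the approval sentence, present in item 47 and absent from item j. Could item 47 be purely an entry rule and 8.3.1 purely an on-study rule? That removes the conflict only if approval depends on stopping the drug before dosing. Neither item 47, item 48 nor 8.3.1 says so. As written, an approved subject who continues the drug breaches item j from the first day of dosing.

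**Row E.** The approval sentence applies to medications listed in Appendix B, and amiodarone is one of them. Exclusion 45 bars recent or current amiodarone outright. The two items are in the same list and give different answers before 8.3.1 is consulted.

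**Item 47 taken alone.** It is an exclusion, under a subheading that calls current use prohibited, followed by a route to approval. The likeliest reading is excluded unless approved, but the reader has to supply the word unless.

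**Size.** The documents give no rate of use of Appendix B drugs in this population, so the number of row C subjects cannot be estimated. For scale only: with about 20 subjects per group, each such subject is 1/20 = 5% of an arm in the safety tables.

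**The case against.** The strongest reply is that the protocol starts from prohibition everywhere and the one exception needs both the Sponsor and the Medical Monitor, so no site can enrol such a subject on its own authority. ECGs are scheduled at screening, on Days 1, 7, 14, 28, 42 and 61, and at follow-up; medications are recorded at every visit. This stands, and it limits the safety consequence. It does not tell an approved subject whether the drug may continue.

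Three stronger readings are tempting, and the documents do not support them.

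- **Section 13.1.3 as a third contradiction.** It says "Protocol waivers will not be granted by the Sponsor in this study", and a reader might infer that it forbids the approval in item 47. It does not. A waiver sets a criterion aside; an approval step written into the criterion is part of it. The protocol uses the same device for CAP scores of >270 to 300 dB/m (inclusion 3), PEth values (exclusion 28) and bilirubin (exclusion 33). Section 13.1.3 bears on the point only in that row C cannot be settled by a waiver. Section 13.1.2 ("Requests for deviations must be made in advance with the Sponsor") does not settle it either.
- **A conflict for every Appendix B drug throughout treatment.** A drug newly started on study falls under 8.3.1(j) alone, which is clear. Many Appendix B entries are also marked as off the US market.
- **Distorted QTcF tables.** Two of the three QTcF categories in SAP 13.5 are increases from baseline, and a stable drug continued from entry would already be reflected in the baseline ECG. The documents give no basis for estimating any effect on the tables.

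The SAP already lists individual medications (Section 10) and all ECG results (Section 13.5) by subject, so affected subjects can be found without a new flag.

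**Conclusion.** The point holds, within limits. Section 8.3.1(j) and exclusion 47 (synopsis item 48) give incompatible answers for a subject who takes an Appendix B drug at entry, is approved and continues it. The amiodarone entries conflict in the same way. Sites cannot comply with both texts, and because the rule concerns cardiac safety this is more than an editorial matter.

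The conclusion rests on the current wording of the protocol and on one reading: that approval under item 47 permits enrolment while the subject is on the drug. If approval was meant to depend on stopping first, the conflict in row C disappears, but the protocol would need to say so. The number of affected subjects is unknown and may be small. The primary efficacy model is not touched. No view is taken here on which rule is clinically right.

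**What to change.** Reconcile Section 7.3 item 47, synopsis item 48 and Section 8.3.1(j), so that one rule, worded the same in all three places, states whether a subject on an Appendix B drug at entry may enrol and whether that drug may continue during treatment. In the same edit, reconcile the amiodarone entries: Appendix B, exclusion 45, synopsis item 46 and 8.3.1(h). The content of the rule is for the sponsor and its medical experts to decide. Section 13.1.3 needs no change.

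The cost is protocol wording. No change to sample size, visits or the analysis model follows. Section 13.1.1 reserves administrative amendments for changes with no impact on subject safety, so the sponsor should consider whether this edit qualifies.

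Optionally, the SAP could mark subjects on an Appendix B drug in the ECG output. SAP Section 10 would count a drug continued from before first dose as prior and not as concomitant, so a mark would make these subjects easier to see. The existing listings already allow them to be identified.
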